6.3.2. Lost to Follow-up

All reasonable efforts must be made to locate subjects to determine and report their ongoing status. This includes follow-up with persons authorized by the subject as noted above. Lost to follow-up is defined by the inability to reach the subject after a minimum of 2 documented phone calls, faxes, or e-mails as well as lack of response by the subject to 1 registered mail letter. All attempts should be documented in the subject's medical records. If it is determined that the subject has died, the site will use locally permissible methods to obtain the date and cause of death. If the investigator's use of a third-party representative to assist in the follow-up portion of the study has been included in the subject's informed consent, then the investigator may use a sponsor-retained third-party representative to assist site staff with obtaining the subject's contact information or other public vital status data necessary to complete the follow-up portion of the study. The site staff and representative will consult publicly available sources, such as public health registries and databases, in order to obtain updated contact information. If, after all attempts, the subject remains lost to follow-up, then the last-known-alive date as determined by the investigator should be reported and documented in the subject's medical records.

6.3.3. Withdrawal for Other Reason:

Subjects may withdraw from the study at any time at their own request, or they may be withdrawn at any time at the discretion of the investigator or sponsor for safety (see also the [Withdrawal From the Study Due to Adverse Events \(see also the Subject Withdrawal/Early Termination section\)](#)) or behavioral reasons, or the inability of the subject to comply with the protocol-required schedule of study visits or procedures at a given study site.

If a subject does not return for a scheduled visit, every effort should be made to contact the subject. All attempts to contact the subject and information received during contact attempts must be documented in the subject's medical record. In any circumstance, every effort should be made to document subject outcome, if possible. The investigator should inquire about the reason for withdrawal, request that the subject return all unused investigational products, request that the subject return for a final visit, if applicable, and follow up with the subject regarding any unresolved adverse events (AEs).

If the subject withdraws from the study, and also withdraws consent for disclosure of future information, no further evaluations should be performed, and no additional data should be collected. The sponsor may retain and continue to use any data collected before such withdrawal of consent.

Subjects who withdraw from the study may be replaced at the discretion of the investigator upon consultation with the sponsor.

6.3.3.1. Discontinuation of Study Treatment with Continued Study Participation

All subjects who discontinue study treatment early will be encouraged to complete the study and follow an abbreviated study visit schedule.

6.3.3.1.1. Discontinuation During Period I Prior to Visit 4

Subjects who discontinue study treatment during Period I prior to Visit 4 will be asked to come to the clinic within seven days of discontinuing study treatment to complete the assessments and procedures outlined in Visit 4 except for: Drug dispensing and dosing, and Assessment during and after subject injection. Subjects should follow-up again 12 weeks (+4 days) later to complete the assessments and procedures that are outlined in Visit 7 except for: Questionnaire administration. Follow up contact will be attempted as described in [Section 6.2.8](#).

6.3.3.1.2. Discontinuation During Period II Prior to Visit 7

Subjects who discontinue study treatment during Period II prior to Visit 7 will be asked to come to the clinic within seven days of discontinuing study treatment to complete the assessments and procedures outlined in Visit 7. Follow up contact will be attempted as described in [Section 6.2.8](#).

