6.2.6. Visit 6 (Study Day 126 \pm 4 days, Week 18)

Visit 6 is at the clinical site and the following procedures and assessments should be made:

- Obtain and record ongoing medications and instruct the subject on the use of concomitant medications ([Section 5.8](#));

- Measure and record vital signs: heart rate, temperature, respiratory rate and blood pressure ([Section 7.2.2](#));
- Conduct brief/limited physical exam ([Section 7.2.4](#));
- Conduct contraception check ([Section 4.4.1](#));
- Collect all used study medication containers (drug accountability);
- Collect all used cartridges and/or injection devices (drug accountability);
- Review and collect subject diary and instruct/provide subject with new subject diary for the remainder of treatment period;
- Injection site assessment;
- Inquire for and record adverse events;
- Inquire for and record injection device complaints;
- Drug Dispensation:
 - Dispense Genotropin to subjects in Sequence 2.
- Inform subject/caregiver of date of next visit and that subject should bring all used and unused study medication containers, used and unused cartridges and/or injection devices, and subject diary to that visit.

6.2.7. Visit 7 (Study Day 168 ±4 days, Week 24) – End of Study Visit

Visit 7 is at the clinical site and is the last visit of the study prior to follow up phone contact.

Subjects who discontinue treatment during Period II but before the end of study visit will be asked to complete the assessments and procedures outlined in Visit 7. The following procedures and assessments should be made:

- Obtain and record ongoing medications;
- Measure and record vital signs: heart rate, temperature, respiratory rate and blood pressure ([Section 7.2.2](#));
- Conduct brief/limited physical exam ([Section 7.2.4](#));
- Conduct contraception check ([Section 4.4.1](#));
- Collect all used and unused study medication containers (drug accountability);

- Collect all used and unused cartridges and/or injection devices (drug accountability);
- Review and collect subject diary;
- Inquire for and record injection site reactions;
- Inquire for and record adverse events;
- Collect fasting (10 hours) specimens for laboratory exams:

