6.3.3.1.3. Treatment of GHD after Discontinuation of Study Treatment

Upon discontinuation of study treatment, subjects should resume standard of care treatment under the direction of the investigator.

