9.1. Sample Size Determination^{19,20}

In order to estimate the sample size, based on solicited internal expert opinion, the following assumptions were considered using a two-sided type-I error of 0.05:

- The expected difference between the two treatment schedules in the Life Interference Total Score is assumed to be from a distribution with mean = 0.45. This is considered to be a moderate effect size.
- The standard deviation of the individual Total Score is assumed to be 1.
- The within-subject correlation of scores measured on a same subject at two different times is assumed to be at least 0.3.

Under these assumptions, a total of 75 subjects are needed at 90% power from a two-sided paired t-test for mean difference for the proposed study using Life Interference as the primary endpoint. As the Life Interference instrument has not been tested in prior clinical trials, the sample size will be increased by approximately 20% to account for the uncertainty in variability of the life interference endpoint and to account for the potential dropouts, increasing the sample size for the study to approximately 90 subjects.

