### **6.2.2. Treatment Experience Assessed using DCOA 2 Questionnaire**

Proportion of Subjects/Caregiver Dyads that select the weekly injection schedule compared to the daily injection schedule in each of the outcome domains below as assessed by the DCOA 2 Questionnaires completed at Week 24, using methods described in [Section 5.2.1](#) and [5.2.3](#):

- Choice of injection pen,
- Preferred injection schedule,
- Convenience of injection schedule,
- Easier to follow,
- Pen ease of use,
- Patient life interference,
- Caregiver life interference, including family life interference,
- Benefit relating to the injection schedule,

- Intention to comply.

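### Dyads that stop weekly somatrogon in Period I are never asked DCOA 2, while those that stop it in Period II are; the weekly-preference proportions may be biased upward, and the SAP does not bound this

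*Protocol*

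**What the plan says.** Protocol 6.3.3.1.1 covers stopping in Period I. The subject attends an early Visit 4 without dispensing or dosing, and 12 weeks later is asked to "complete the assessments and procedures that are outlined in Visit 7 except for: Questionnaire administration". Visit 4 (6.2.4) includes DCOA 1 and PGIS-IDA only. DCOA 2 is given only after Period II (Section 3, Appendix 5), and no other section restores it for these dyads.

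For stopping in Period II, Section 6.2.7 says: "Subjects who discontinue treatment during Period II but before the end of study visit will be asked to complete the assessments and procedures" of Visit 7. Section 6.3.3.1.2 agrees and makes no exception for questionnaires. Visit 7 contains DCOA 1, DCOA 2 and PGIS-IDA.

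After stopping, 6.3.3.1.3 says: "Upon discontinuation of study treatment, subjects should resume standard of care treatment under the direction of the investigator".

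The DCOA 2 endpoint in SAP 6.2.2 is the "Proportion of Subjects/Caregiver Dyads that select the weekly injection schedule compared to the daily injection schedule", domain by domain, at Week 24. SAP 5.2.1 asks for the number of non-missing observations, the observed proportion and a Wilson interval. SAP 5.3 does not impute missing outcomes. SAP 5 sets the population count (header N) as the percentage denominator unless something else is specified. The sensitivity analyses in SAP 6.1.1.2 concern only the primary endpoint.

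**The concern.** The rule is written by period, but its effect on dyads that stop weekly treatment depends on sequence. Sequence 1 takes weekly second, so a dyad that stops it is asked which schedule it prefers. Sequence 2 takes weekly first, so a dyad that stops it is never asked, although it is invited back to the clinic 12 weeks later.

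Lack of experience does not explain the omission for Sequence 2. These dyads have used weekly. Inclusion criterion 2 requires at least 3 months of prior growth hormone by pen, which the study design describes as daily.

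Preference for the weekly schedule is part of the study's stated argument about later adherence (Protocol 1.2). If the unasked dyads tend to prefer daily, leaving them out raises the reported weekly preference, and no planned analysis would show it. The same dyads also give no later DCOA 1 or PGIS-IDA score to set beside their weekly one.

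**Working it through.** **1. What each kind of stopper is asked after baseline**

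| Dyad stops | Sequence | Used weekly? | DCOA 1 | DCOA 2 |
|---|---|---|---|---|
| weekly, Period I | 2 | yes | once, early Visit 4 | never |
| weekly, Period II | 1 | yes | Visit 4 and Visit 7 | yes |
| daily, Period I | 1 | no | once, early Visit 4 | never |
| daily, Period II | 2 | yes | Visit 4 and Visit 7 | yes |

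PGIS-IDA follows the DCOA 1 column. In the third row the omission of DCOA 2 is defensible: exclusion criterion 10 bars prior long-acting growth hormone, so these dyads have nothing to compare. The gap is the first row.

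**2. The plan's own figure, and the effect on primary power**

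Inputs from Protocol 9.1: two-sided alpha 0.05; a mean difference of 0.45; an SD of 1 for a single score; and, for the pairing, "The within-subject correlation of scores measured on a same subject at two different times is assumed to be at least 0.3".

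- SD of the paired difference = √(2 × (1 − 0.3)) = 1.183.
- Two-sided paired t-test, noncentral t: n = 75 gives power 0.902, which reproduces the stated 75. 75 × 1.2 = 90 reproduces the total.
- Treating each Period I weekly stopper as a lost pair: 90, 88, 85 and 81 pairs give power 0.946, 0.942, 0.934 and 0.922.

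Power is not the issue.

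**3. Size of the selection effect on DCOA 2**

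Assumptions, none of them in the documents: 90 dyads; k Sequence 2 dyads stop weekly in Period I; a proportion p of the others and q of the stoppers would choose weekly; no other missing data.

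- Reported with a non-missing denominator: p.
- If everyone were asked: [p(90 − k) + qk] / 90.
- Excess = (k/90)(p − q).

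With p = 85% and q = 0:

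| k | Reported | All asked | Excess (points) |
|---|---|---|---|
| 2 | 85.0% | 83.1% | 1.9 |
| 4 | 85.0% | 81.2% | 3.8 |
| 6 | 85.0% | 79.3% | 5.7 |
| 9 | 85.0% | 76.5% | 8.5 |

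With q = 85% the excess is zero for every k.

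The sequences also separate. Suppose 36 of 45 dyads in each sequence (80%) truly choose weekly, and 5 Sequence 2 dyads that would choose daily are not asked. Sequence 2 then reads 36/40 = 90% against 36/45 = 80% in Sequence 1.

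**4. Dependence on the denominator**

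Under header N the reported figure is p(90 − k)/90, because unasked dyads count as not selecting weekly. If q = 0 this equals the all-asked column and the excess disappears. If q is above 0 it understates weekly preference by qk/90. With q = 85% that is 1.9 points for k = 2 and 8.5 points for k = 9. SAP 5.2.1 and 5.3 point to non-missing responses and SAP 5 points to header N; SAP 6.2.2 does not choose.

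**The case against.** A reader might infer that the plan certainly overstates weekly preference. The documents do not support that. Subjects can stop for adverse events, behavioural reasons, inability to keep visits, non-compliance or inability to use the device, and nothing shows that they would choose daily. The direction also needs a non-missing denominator, which the SAP leaves unclear. The counts of 2 to 9 have no source: the roughly 20% inflation in Protocol 9.1 covers variance uncertainty and dropout together, and Protocol 1.3 reports no discontinuations for adverse events in the Phase 2 paediatric study. All of this stands, and it makes the bias conditional.

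A reader might also infer that the primary endpoint is compromised. It is not, to any important degree. These dyads give one DCOA 1 score, the model uses available data on the full analysis set, and power stays at 0.92 or above with 9 pairs lost. SAP 5 does say that early-discontinuation measurements will be listed, without saying whether they enter the model.

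The consequence is also modest in statistical terms. DCOA 2 is secondary and summarised with intervals. For 73 of 86 respondents the 95% Wilson interval is about 76% to 91%, which contains the 81% that applies when k = 4. But that interval describes sampling error and does not account for selection.

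Finally, DCOA 2 is defined after two study periods. An early answer may follow a short weekly exposure and rest partly on pre-study treatment, which for some US subjects used a different pen. The redacted items cannot be checked for fit. This is a good reason not to pool early answers with Week 24 answers. It is not a reason to leave them uncollected.

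**Conclusion.** The asymmetry is in the text: dyads that stop weekly somatrogon are asked DCOA 2 in Sequence 1 and not in Sequence 2, and nothing elsewhere in the plan repairs or bounds it. Upward bias follows only if these Sequence 2 dyads favour weekly less than the others and the denominator is non-missing responses. On the assumptions shown, with all stoppers choosing daily, it is 1.9 to 8.5 points. The same rule also removes Sequence 1 dyads that stop daily in Period I, but they cannot make the comparison. This is a worthwhile improvement to secondary endpoints. It does not threaten the primary result.

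**What to change.** 1. **Protocol 6.3.3.1.1**, with 6.2.4 and Appendix 5 made consistent. For Sequence 2 subjects who received somatrogon, administer the schedule-preference items of DCOA 2 at the early Visit 4. Administer DCOA 1 and PGIS-IDA at the retained 12-week visit, flagged as off-study standard of care.
2. **SAP 6.2.2.** State the DCOA 2 denominator. Keep Week 24 respondents as the main analysis. Add two supportive rows: one that includes the flagged early-stopper responses, and one that counts Period I weekly stoppers as not selecting weekly.
3. **SAP 6.1.1.2.** Use the extra DCOA 1 score only in a sensitivity analysis of the primary endpoint.

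The cost is protocol and SAP wording, an ePRO configuration change and questionnaires for a few dyads. Protocol 11.1.1 puts the full set at 30 to 40 minutes per time point. No visit is added. The drawback is that early answers rest on shorter weekly exposure and partly on pre-study daily experience; the flag discloses this.

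If collection can no longer change, the denominator statement and the row counting Period I weekly stoppers as not selecting weekly are enough to bound the bias.

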6.3.3.1.3. Treatment of GHD after Discontinuation of Study Treatment

Upon discontinuation of study treatment, subjects should resume standard of care treatment under the direction of the investigator.

7. ASSESSMENTS

Every effort should be made to ensure that the protocol-required tests and procedures are completed as described. However, it is anticipated that from time to time there may be circumstances outside of the control of the investigator that may make it unfeasible to perform the test. In these cases the investigator will take all steps necessary to ensure the safety and well-being of the subject. When a protocol-required test cannot be performed, the investigator will document the reason for this and any corrective and preventive actions that he or she has taken to ensure that normal processes are adhered to as soon as possible. The study team will be informed of these incidents in a timely manner.

For samples being collected and shipped, detailed collection, processing, storage, and shipment instructions and contact information will be provided to the investigator site prior to initiation of the study.

7.1. Pregnancy Testing

For female subjects of childbearing potential, a urine pregnancy test, with sensitivity of at least 25 mIU/mL, will be performed at screening, before investigational product administration at the baseline visit, at Visit 4 & 7 (end of the study visit) to confirm the subject has not become pregnant during the study, and at the early-withdrawal visit (if applicable).

A negative pregnancy test result is required before the subject may receive the investigational product. Pregnancy tests will also be done whenever 1 menstrual cycle is missed during the active treatment period (or when potential pregnancy is otherwise suspected). Pregnancy tests may also be repeated if requested by institutional review boards (IRBs)/ethics committees (ECs) or if required by local regulations. A positive urine pregnancy test will be confirmed with a serum pregnancy test.

In the case of a positive confirmed pregnancy, the subject will be withdrawn from administration of investigational product and from the study.

Urine pregnancy tests must be sensitive to at least 25 mIU/mL and will be conducted with the test kit provided by the central laboratory in accordance with instructions provided in its package insert. Subjects who have missed a menstrual period or who show an indeterminate or positive result on the urine test may not further progress in the study until pregnancy is ruled out using further diagnostic testing (eg, a negative quantitative serum pregnancy test conducted at a certified laboratory).

7.2. Safety

7.2.1. Laboratory

Laboratory tests for safety will be performed at times defined in the [Schedule of Activities](#) of this protocol. Subject eligibility based on these tests will be determined at screening.

7.2.1.1. Local Laboratory Tests

Urine pregnancy test will be performed locally using the kits provided by the central lab. If local urine pregnancy testing is positive, serum pregnancy tests should be submitted to the central laboratory.

7.2.1.2. Central Laboratory Tests

A central laboratory will be used to analyze hematology, blood chemistry, liver function, thyroid function, and urinalysis tests (as listed in [Table 1](#) below), as well as hormones and to ensure accuracy and consistency in test results. The central laboratory will transmit all results for protocol tests, scheduled and unscheduled, to the sponsor for inclusion in the clinical data base. Urinalysis will be performed on mid-stream, clean catch specimens.

The following safety laboratory tests will be performed at times defined in the [Schedule of Activities](#) and [STUDY PROCEDURES](#) sections of this protocol.

Table 1. Laboratory Tests

Hematology	Chemistry	Liver Function	Lipid Profile	Urinalysis	Additional
Hemoglobin	BUN	AST	Total Cholesterol	pH	IGF-I
Hematocrit	Creatinine	ALT	HDL Cholesterol	Specific gravity	IGF-I SDS
Red blood cell (RBC) count	BUN/Creatinine Ration	GGT	LDL Cholesterol	Bilirubin	Hemoglobin A1c
Mean cell volume (MCV)	Glucose	Total bilirubin	VLDL	Nitrite	Free thyroxine (FT4)
Mean cell hemoglobin (MCH)	Ca ⁺⁺	Direct bilirubin	Cholesterol	Leukocyte Esterase	Urine pregnancy (WOCBP)
Mean cellular hemoglobin concentration (MCHC)	Na ⁺ , K ⁺ , Cl	Indirect bilirubin	Triglycerides	Glucose (qual)	Serum pregnancy (if needed for WOCBP)
Platelet count	Total CO ₂ (Bicarbonate)	Alkaline phosphatase		Protein (qual)	Somatrogon Level
White blood cell (WBC) count	Uric acid			Blood (qual)	Anti-somatrogon Ab (and neutralizing Ab)
Total neutrophils (Absolute [Abs])	Albumin			Ketones	Anti-rhGH Ab (and neutralizing Ab)
Eosinophils (Abs)	Total protein			Microscopic (if necessary)	
Monocytes (Abs)	LDH				
Basophils (Abs)	Magnesium				
Lymphocytes (Abs)	Phosphorus				
	CK				
	GFR				

7.2.2. Vital Signs

Temperature, heart rate (HR), Respiratory Rate (RR) and blood pressure (BP) will be measured at times specified in the [Schedule of Activities](#) of this protocol. Additional collection times, or changes to collection times of HR, RR, and BP will be permitted, as necessary, to ensure appropriate collection of safety data.

Sitting BP will be measured with the subject's arm supported at the level of the heart, and recorded to the nearest mm Hg after 5 minutes of rest. The same arm (preferably the dominant arm) will be used throughout the study. The same size BP cuff, which has been properly sized and calibrated, will be used to measure BP each time. The use of automated devices for measuring BP and PR is preferred, although when done manually, PR will be measured in the brachial/radial artery for at least 30 seconds. When the timing of these measurements coincides with a blood collection, BP and PR should be obtained prior to the nominal time of the blood collection.

7.2.3. Weight and Height

Height will be measured without shoes according to the [Schedule of Activities](#).

Body weight will be measured according to the [Schedule of Activities](#) in indoor clothing without shoes.

7.2.4. Physical Exam

Physical exam will be performed according to the [Schedule of Activities](#).

Complete Physical Examination

The following parameters and body systems will be examined and any abnormalities described: General appearance, weight and height, skin (presence of rash), HEENT (head, eyes, ears, nose and throat), lungs (auscultation), heart (auscultation for presence of murmurs, gallops, rubs), lower extremities (peripheral edema), abdominal (palpation and auscultation), neurologic (mental status, station, gait, reflexes, motor and sensory function, coordination) and lymph nodes.

Brief/Limited Examination

An abbreviated physical examination will be performed assessing the following: examination of heart, lungs, lower extremities for peripheral edema, abdomen and lymph nodes. Any clinically significant changes from the baseline examination should be recorded as AEs.

